**Investigator Interests:**

Does the principal investigator, or do any research personnel who are responsible for the design, conduct or reporting of this project or any of their family members (spouse or dependent child) have an incentive or interest, financial or otherwise, that may affect the protection of the human subjects involved in this project, the scientific objectivity of the research or its integrity? Note: The Principal Investigator (Project Director), upon consideration of the individual's role and

degree of independence in carrying out the work, will determine who is responsible for the design, conduct, or reporting of the research.

See Disclosures and Management of Personal Interests in Human Research

<http://www.yale.edu/hrpp/policies/index.html#COI>

Yes       No

Do you or does anyone on the research team who is determined by you to be responsible for the design, conduct or reporting of this research have any patent (sole right to make, use or sell an invention) or copyright (exclusive rights to an original work) interests related to this research protocol?

Yes       No

If yes to either question above, list names of the investigator or responsible person:

*The Yale University Principal Investigator, all Yale University co-investigators, and all Yale University individuals who are responsible for the design, conduct or reporting of research must have a current financial disclosure form on file with the University's Conflict of Interest Office. Yale New Haven Hospital personnel who are listed as co-investigators on a protocol with a Yale University Principal Investigator must also have a current financial disclosure form on file with the University's Conflict of Interest Office. If this has not been done, the individual(s) should follow this link to the COI Office Website to complete the form:*

<http://www.yale.edu/coi/>

**NOTE:** The requirement for maintaining a current disclosure form on file with the University's Conflict of Interest Office extends primarily to Yale University and Yale-New Haven Hospital personnel. **Whether or not they are required to maintain a disclosure form with the University's Conflict of Interest Office, all investigators and individuals deemed otherwise responsible by the PI who are listed on the protocol are required to disclose to the PI any interests that are specific to this protocol.**

## SECTION II: GENERAL INFORMATION

**1. Performing Organizations:** Identify the hospital, in-patient or outpatient facility, school or other agency that will serve as the location of the research. Choose all that apply:

**a. Internal Location[s] of the Study:**

- |  |   |
|--|---|
|  Magnetic Resonance Research Center
(MR-TAC) |  Yale University PET Center                         |
|  Yale Cancer Center/Clinical Trials Office (CTO)           |  YCCI/Church Street Research Unit (CSRU) |
|  Yale Cancer Center/Smilow                                 |  YCCI/Hospital Research Unit (HRU)       |
|  Yale-New Haven Hospital                                   |  YCCI/Keck Laboratories                             |
|  Cancer Data Repository/Tumor Registry                     |  Yale-New Haven Hospital—Saint Raphael Campus       |
|  Specify Other Yale Location:                              |   |

**b. External Location[s]:**

 APT Foundation, Inc.	 Haskins Laboratories
 Connecticut Mental Health Center	 John B. Pierce Laboratory, Inc.
 Clinical Neuroscience Research Unit (CNRU)	 Veterans Affairs Hospital, West Haven
 Other Locations, Specify:  (Specify location(s)):	 International Research Site

**c. Additional Required Documents (check all that apply):**

- |  |                              |
|--|------------------------------|
|  *YCCI-Scientific and Safety Committee (YCCI-SSC)   |  N/A |
|  *Pediatric Protocol Review Committee (PPRC)   | Approval Date: 2/23/2016     |
|  *YCC Protocol Review Committee (YRC-PRC)  | Approval Date:               |
|  *Dept. of Veterans Affairs, West Haven VA HSS   | Approval Date:               |
|  *Radioactive Drug Research Committee (RDRC)   | Approval Date:               |
|  YNHH-Radiation Safety Committee (YNHH-RSC)  | Approval Date:               |
|  Magnetic Resonance Research Center PRC (MRRC-PRC)  | Approval Date: 3/19/2016     |
|  YSM/YNHH Cancer Data Repository (CaDR)  | Approval Date:               |
|  Dept. of Lab Medicine request for services or specimens form  |                              |
|  Imaging on YNHH Diagnostic Radiology equipment request form (YDRCTO request) found at http://radiology.yale.edu/research/ClinTrials.aspx |                              |

*\*Approval from these committees is required before final HIC approval is granted. See instructions for documents required for initial submission and approval of the protocol. Allow sufficient time for these requests. Check with the oversight body for their time requirements.*

2. **Probable Duration of Project:** State the expected duration of the project, including all follow-up and data analysis activities. 7years

3. **Research Type/Phase: (Check all that apply)**

**a. Study Type**

- Single Center Study  
 Multi-Center Study

Does the Yale PI serve as the PI of the multi-site study? Yes  No

- Coordinating Center/Data Management  
 Other:

**b. Study Phase**  N/A

- Pilot  Phase I  Phase II  Phase III  Phase IV  
 Other (Specify)

4. **Area of Research: (Check all that apply)** Note that these are overlapping definitions and more than one category may apply to your research protocol. Definitions for the following can be found in the instructions section 4c:

- Clinical Research: Patient-Oriented  
 Clinical Research: Epidemiologic and Behavioral  
 Translational Research #1 ("Bench-to-Bedside")

- Clinical Research: Outcomes and Health Services  
 Interdisciplinary Research

Translational Research #2 (“Bedside-to-Community”)  Community-Based Research

5. Is this study a clinical trial? Yes  No

*NOTE the current ICMJE (International Committee of Medical Journal Editors) definition of a clinical trial: “any research study that prospectively assigns human participants or groups of humans to one or more health-related interventions to evaluate the effects on health outcomes.” Health-related interventions include any intervention used to modify a biomedical or health-related outcome (for example, drugs, surgical procedures, devices, behavioral treatments, dietary interventions, and process-of-care changes). Health outcomes include any biomedical or health-related measures obtained in patients or participants, including pharmacokinetic measures and adverse events”*

If yes, where is it registered?

Clinical Trials.gov registry: NCT03469492

:

Other (Specify)

Registration of clinical trials at their initiation is required by the FDA, NIH and by the ICMJE.

*If this study is registered on clinicaltrials.gov, there is new language in the consent form and compound authorization that should be used.*

For more information on registering clinical trials, including whether your trial must be registered, see the YCCI webpage, <http://ycci.yale.edu/researchers/ors/registerstudy.aspx> or contact YCCI at [contact])

6. Does the Clinical Trials Agreement (CTA) require compliance with ICH GCP (E6)?

Yes  No

7. Will this study have a billable service? A Billable Service is defined as a service or procedure that will be ordered, performed or result in charging in EPIC for individuals who are enrolled in a clinical research study, regardless if the charge is intended to be paid by the subject/their insurance or the research study.

Yes  No

If you answered "yes", this study will need to be set up in OnCore Support

<http://medicine.yale.edu/ymg/systems/ppm/index.aspx>

8.. Are there any procedures involved in this protocol that will be performed at YNHH or one of its affiliated entities? Yes    No    *If Yes, please answer questions a through c and note instructions below. If No, proceed to Section III.*

a. Does your YNHH privilege delineation currently include the **specific procedure** that you will perform? Yes

b. Will you be using any new equipment or equipment that you have not used in the past for this procedure? No

- c. Will a novel approach using existing equipment be applied? No

If you answered "no" to question 7a, or "yes" to question 7b or c, please contact the YNHH Department of Physician Services ([name]) for prior approval before commencing with your research protocol.

### SECTION III: FUNDING, RESEARCH TEAM AND TRAINING

- Funding Source:** Indicate all of the funding source(s) for this study. Check all boxes that apply.  
Provide information regarding the external funding source. This information should include identification of the agency/sponsor, the funding mechanism (grant or contract), and whether the award is pending or has been awarded. Provide the M/C# and Agency name (if grant-funded). If the funding source associated with a protocol is "pending" at the time of the protocol submission to the HIC (as is the case for most NIH submissions), the PI should note "Pending" in the appropriate section of the protocol application, provide the M/C# and Agency name (if grant-funded) and further note that University (departmental) funds support the research (until such time that an award is made).
- Research Team:** List all members of the research team. Indicate under the affiliation column whether the investigators or study personnel are part of the Yale faculty or staff, or part of the faculty or staff from a collaborating institution, or are not formally affiliated with any institution. **ALL members of the research team MUST complete Human Subject Protection Training (HSPT) and Health Insurance Portability and Accountability Act (HIPAA) Training before they may be listed on the protocol.** See NOTE below. This information is maintained in IRES

**NOTE: The HIC will remove from the protocol any personnel who have not completed required training. A personnel protocol amendment will need to be submitted when training is completed.**

### SECTION V: RESEARCH PLAN

- Statement of Purpose:** State the scientific aim(s) of the study, or the hypotheses to be tested.  
Growing evidence suggests that fructose is linked to the development of obesity and diabetes. Studies investigating the central nervous system (CNS) effects of fructose have shown that fructose and glucose have distinct metabolic effects in the brain. While intraventricular glucose infusion into the brain decreases feeding in rodents, intraventricular fructose infusion has the opposite effect to promote feeding. Moreover, our research group has shown using functional MRI in humans that ingestion of fructose and glucose has differential effects on cerebral blood flow in specific brain regions that influence eating behavior.

Recently, we have found that glucose is converted to fructose in the CNS via the polyol pathway (glucose→sorbitol→fructose). We found that fasting cerebrospinal fluid (CSF) fructose levels obtained at the time of spinal anesthesia in pregnant women undergoing elective

caesarean section are nearly 20-times higher than plasma levels. CSF sorbitol levels were also nearly 10-fold greater than plasma levels further supporting the presence of an active polyol pathway in the CNS. Furthermore, CSF fructose levels correlated positively with CSF glucose levels ( $p = 0.453$ ,  $p = 0.02$ ).

**Specific Aim:** To investigate whether longer-term improvement of glycemic control in poorly controlled diabetes patients with a 12-week intensification of their diabetic treatment regimen will lead to decreased polyol pathway activity.

**Hypothesis:** Polyol pathway activity will decrease in diabetic individuals who undergo intensification of their diabetes treatment regimens as reflected by lower baseline brain intracellular fructose levels and higher intracellular glutathione levels. Furthermore, following longer-term improved glycemic control, patients may also have down-regulation of the pathway as reflected by decreased production of intracellular fructose in response to hyperglycemic clamp.

15 T2DM subjects and 15 T1DM subjects with chronic hyperglycemia (HbA1C > 7.5%) will participate in a 12-week intervention study aimed at reducing their A1C levels. By lowering their glucose levels, we expect to also decrease activity through the polyol pathway. Subjects will receive exercise and dietary counseling in accordance to guidelines established by the American Diabetes Association. In addition, all patients will have their diabetes regimens adjusted on a weekly basis to achieve a target blood glucose level based upon data from the patients performing self-monitoring of blood glucose (SMGB).

At 0 and 12 weeks, subjects will undergo baseline MRS scan at 4T to measure intracerebral glucose, fructose, and glutathione. Participants may also be invited to participate in an overnight admission to normalize blood glucose levels, and a hyperglycemic clamp. During each of these two scans, plasma glucose, fructose, insulin, HbA1c, and fructosamine levels will be measured concurrently. One week prior to the week 0 and week 12 MRS scans, subjects will be asked to wear a CGMS (Free style libre) to continuously monitor their interstitial blood glucose levels and record their food intake in a food log. After first placing the CGM prior to the week 0 scan, the system is removed after 14 days and then reinserted for 14 days before the week 12 MRS scan.

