**Optional Hyperglycemic clamp:**

Prior to MRS scanning at weeks 0 and 12 Subjects may also be invited to participate in an optional overnight admission to normalize blood glucose levels the night before scanning and then a hyperglycemic clamp the following morning.

Subjects will be admitted in the evening prior to MRS scan day (~ 6 PM) to the YNHH research unit, all of their diabetic medications will be held and they will be placed on an insulin drip beginning at 8PM to maintain blood sugar levels at ~90-100 mg/dl until 7AM the next morning. The next morning, participants will be taken to the MRRC for MRS scanning. Following the 45 minute

baseline scan, subjects will remain in the scanner for continuous scanning during the hyperglycemic clamp (see figure). An infusion of 20% dextrose at a variable rate to maintain plasma glucose levels at 220 mg/dL for 4 hours. Glucose infusion rates will be adjusted in response to plasma glucose levels measured every 5-10 minutes. Subjects will be able to take breaks as needed during the 3 hours hyperglycemic clamp and MRS scan. At baseline, 2 and 4 hours, plasma samples will also be obtained for fructose, sorbitol, insulin levels and other hormonal markers.

**Continuous glucose monitoring system (CGMS) and Food logs (at -1, and 11 weeks):** One week prior to the MRS scans at 0 and 12 weeks, subjects will be asked to wear a CGMS (Free style libre) to continuously monitor their interstitial blood glucose levels and record their food intake

**Blood collection for platelet and inflammation analysis:** Participants will also have blood collected (~80 cc) for analysis of polyol pathway activity in platelets as well as for changes in inflammatory markers such as cytokines IL-6, TNF-alpha at weeks 0, and 12 weeks.

**Optional Specimens for Future Storage:** Subjects will be asked to give permission for the storage of any blood obtained during the study that will not be used for the above noted analysis

**4. Genetic Testing** N/A

**5. Subject Population:** Provide a detailed description of the types of human subjects who will be recruited into this study.

15 T2DM subjects with HbA1C > 7.5%

15 T1DM subjects with HbA1C > 7.5%

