The 12-week intensification of diabetes management poses minimal risks to the patient. All medical management strategies will follow the general strategies outlined in the Position Statement of the American Diabetes Association and the European Association for the Study of Diabetes [48]. There may be slightly increased risk of hypoglycemia with improved glycemic control; however, as patients are all poorly controlled T2DM patients and we are targeting blood glucose levels to between 80-140 mg/dl before meals and between 100-160 mg/dl at bedtime, we expect that this risk will be minimal. Subjects will be provided with free style libre sensors throughout the study (9 sensors are provided during the 12 weeks that the study last), and free style libre continuous glucose monitor reader. All participants will receive exercise and dietary counseling in accordance with ADA guidelines and increased frequency of medical attention to lower their blood glucose to target ranges. Throughout the study, individuals will be contacted via telephone call or through additional clinic visits as deemed necessary for maintenance of glycemic control. All individuals will receive education regarding the detection and proper management of hypoglycemia.

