**Plan for reporting adverse events to co-investigators on the study, as appropriate the protocol's research monitor(s)**

For the current study, the following individuals, funding, and/or regulatory agencies will be notified (choose those that apply):

All Co-Investigators listed on the protocol.

National Institutes of Health

The principal investigator ([name]) will conduct a review of all adverse events upon completion of every study subject. The principal investigator will evaluate the frequency and severity of the adverse events and determine if modifications to the protocol or consent form are required.

**12. Statistical Considerations:** Describe the statistical analyses that support the study design.

**Primary endpoints:** Primary endpoints include (a) HbA1C levels and CGM measures of glycemia; (b) baseline intracellular fructose and glutathione levels at 0, and 12 weeks; (c) intracellular fructose and glutathione levels following hyperglycemic clamp at 0 and 12 weeks.

**Secondary endpoints:** Concentrations of hormones and polyol metabolites will be correlated with structural changes/inflammatory changes on MRI.

**Sample size:** Because endogenous intracellular fructose production in the brain has never been shown in humans, the studies described in this proposal are exploratory studies. As such, sample sizes and statistical comparisons may not provide adequate power for definitive hypothesis testing. Because intracellular polyol levels will likely be equal to or higher than CSF levels, we expect that the percentage changes as measured by MRS will match those (or be even larger) than observed in CSF.

**Statistical analysis:** Before statistical testing, all variables will be tested for normality of distribution. For between-group comparison, ANOVA and t-tests will be used for continuous variables. Within subject comparisons at baseline and following hyperglycemia will be made with paired t-tests (parametric) and Mann-Whitney U (non-parametric) as well as repeated measures ANOVA as appropriate.

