## SECTION X: RESEARCH ALTERNATIVES AND ECONOMIC CONSIDERATIONS

1. **Alternatives:** What other alternatives are available to the study subjects outside of the research? The alternative is to decline participation in the study.
2. **Payments for Participation (Economic Considerations):** Describe any payments that will be made to subjects, the amount and schedule of payments, and the conditions for receiving this compensation.

\$25 for the screening visit

\$50 for wearing the CGMS at week -1

\$150 for overnight admission/Hyperglycemic clamp/MRS scans at week 0 (Optional)

\$50 for wearing the CGMS at week 11

\$325 for overnight admission/Hyperglycemic clamp/MRS scans at week 12 (Optional)

Payments will be given via a Bank of America pre-paid debit card using the new Yale electronic payment service. After the first payment milestone (first study visit) subjects will receive a card in the mail which will need to be activated over the phone, any subsequent milestones

payments will automatically add additional funds to the subject's card. Reimbursement for incidental expenses will also be provided.

**3. Costs for Participation (Economic Considerations):** Clearly describe the subject's costs associated with participation in the research, and the interventions or procedures of the study that will be provided at no cost to subjects.

The medical evaluation including physical examination and study related laboratory work will be performed at no additional cost to the study participant.

**4. In Case of Injury:** This section is required for any research involving more than minimal risk.

- a. Will medical treatment be available if research-related injury occurs?
- b. Where and from whom may treatment be obtained?
- c. Are there any limits to the treatment being provided?
- d. Who will pay for this treatment?
- e. How will the medical treatment be accessed by subjects?

Medical treatment will be offered to the subjects for any physical injuries that they receive because of participating in this research. Yale School of Medicine and Yale-New Haven Health does not provide funds for treatment of research-related injury. However, the subject or his/her insurance company is responsible for the cost. Federal regulations require that subjects be told that if they are physically injured, no additional financial compensation is available. Subjects do not give up any legal rights by signing the consent form.

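### Does the unstated CGM analysis window in primary endpoint (a) distort the week 0 to week 12 change in glycemia?

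*Combined protocol and SAP*

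**What the plan says.** Section V.12 (Statistical Considerations) gives "HbA1C levels and CGM measures of glycemia" as the first of three groups of primary endpoints. It names no CGM metric, days, minimum wear or excluded hours. It also calls the work exploratory and gives no power calculation.

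Four places describe the wear:

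- Section V.1 (Statement of Purpose) dates both periods: "One week prior to the week 0 and week 12 MRS scans, subjects will be asked to wear a CGMS". It then gives their length: "After first placing the CGM prior to the week 0 scan, the system is removed after 14 days and then reinserted for 14 days", the second period being placed before the week 12 scan.
- Section V.3 (Research Plan) titles its paragraph "Continuous glucose monitoring system (CGMS) and Food logs (at -1, and 11 weeks".
- Section X.2 (Payments) pays for wear at week -1 and again "for wearing the CGMS at week 11".
- Section V.10 (Minimizing Risks) says: "Subjects will be provided with free style libre sensors throughout the study (9 sensors are provided during the 12 weeks that the study last".

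Two further statements matter. On treatment, Section V.1 says "all patients will have their diabetes regimens adjusted on a weekly basis", guided by self-monitored glucose. On the optional admission, Section V.3 says of participants that "they will be placed on an insulin drip beginning at 8PM to maintain blood sugar levels at ~90-100 mg/dl until 7AM the next morning". A baseline scan of about 45 minutes and a clamp at 220 mg/dL follow. The clamp is given as 4 hours in one sentence and 3 hours in another.

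**The concern.** Three features look troublesome together.

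- A 14-day wear that starts a week before week 0 ends a week after it. If all 14 days were called baseline, half of the baseline would come from the treatment period.
- The second wear can be read as 14 days ending at the scan, or as a wear starting at week 11. These imply different follow-up days.
- The overnight drip and the clamp impose glucose levels for many hours immediately before and on the scan day, in some subjects only, and no text removes those hours.

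No control group is described, so the within-subject change from week 0 to week 12 is the evidence that glycemia improved. A contaminated window would mostly shrink that change, and no comparator would offset it. An unwritten window also leaves room to choose one after the data are seen.

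**Working it through.** The plan gives no CGM mean, standard deviation or expected change, so there is no planned figure to reproduce. The check uses day counts and shares of hours. All percentages refer to mean glucose; they do not carry over to time in range or variability.

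**1. Which days every reading covers.** The start dates come from Sections V.1, V.3 and X.2, the 14-day length from Section V.1.

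- First wear: -7 + 14 = day +7, so 7/14 = 50% of it falls after week 0. It contains days -7 to 0.
- Second wear: days 70-84 (14 days ending at the scan), 77-84 (week 11 to the scan) or 77-91 (14 days from week 11). All three contain days 77-84.
- Sensors throughout: week -1 to week 12 is 91 days, or 91/14 = 6.5 sensors if each lasts 14 days (assumed). Two separate wears need 2, and 9 are supplied. This is a supply question; continuous wear would also contain both pre-scan weeks.

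Seven days before each scan are therefore available under every reading.

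**2. Days 0 to +7 counted as baseline.** Assume that all 14 days are averaged, that treatment starts on day 0 (implied, not stated), and that the effect rises linearly to its full size at day T. The mean effect over days 0-7 is 3.5/T of the full effect, and these days are half of the window:

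bias = 0.5 × 3.5/T

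| T | Understatement, share of full effect |
|---|---|
| 14 days | 12.5% |
| 28 days | 6.25% |
| 56 days | 3.1% |
| 84 days | 2.1% |

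For T = 84 the mean effect over days 77-84 is 80.5/84 of the full effect, so the bias is about 2.2% of the measured change.

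Sections V.1 and V.3 have glucose records reviewed weekly to guide adjustment. If recording starts at week 0 (not stated), the first data-guided change comes around day 7, when the first sensor comes off. The bias is then 0%, apart from any early effect of counselling. With days -7 to 0 as baseline it is 0% for any T.

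**3. Admission hours left in the window.** The drip lasts 11 h (8 PM to 7 AM), the baseline scan 0.75 h, the clamp 3 or 4 h.

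- Total: 11 + 0.75 + 3 = 14.75 h, or 11 + 0.75 + 4 = 15.75 h.
- Share p of 7 days (168 h): 14.75/168 = 8.8% to 15.75/168 = 9.4%.
- Share p of 14 days (336 h): 4.4% to 4.7%.
- If the sensor is off in the magnet, only the drip counts: 11/168 = 6.5%, or 11/336 = 3.3%.

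Let U be usual mean glucose and G the imposed mean. The window mean is (1 - p)U + pG. G has the same targets at both visits, so for a subject clamped twice it cancels, and the measured change is (1 - p) times the true change. It shrinks by p.

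A subject clamped at one visit only is different. Assume usual means of 200 falling to 150 mg/dL, 7-day windows, a 4 h clamp, and 95 mg/dL during the drip and baseline scan:

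- Week 0 only: (11.75 × (95 - 200) + 4 × (220 - 200))/168 = -6.87 mg/dL. The change shrinks by 6.87/50 = 13.7%.
- Week 12 only: (11.75 × (95 - 150) + 4 × (220 - 150))/168 = -2.18 mg/dL. The change grows by 2.18/50 = 4.4%.

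**4. Group level.** If a fraction f of subjects is clamped at both visits, the mean change shrinks by f × p. The largest value, f = 1 with the longer clamp, is 9.4%, or 0.094 × 50 = 4.7 mg/dL of the assumed 50 mg/dL fall. The fraction f is not stated. If the window ends at the evening admission (about 6 PM the day before), the effect is zero.

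**The case for a change.** The strongest case for a change is that an exploratory label excuses low power, not an undefined primary endpoint. The drip and clamp hours do not simply cancel, because fixed imposed values replace usual values that are expected to fall. The distortion differs between subjects, since the admission is optional. The window could be stated in a sentence at no cost in data, which would remove any post hoc choice.

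Much of this is true as description. The metric and days are unwritten, the wear descriptions do not agree, and imposed hours in a window through the scan would attenuate the change in mean glucose. What does not stand is the inference that the result is at risk. The dated CGM entries all point to the week before each scan, so days 0 to +7 are not the natural baseline. The two dates for the second wear depend on reading an ambiguous phrase as 14 days ending at the scan; it can equally give only the length of a wear started at week 11.

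Whether clamp hours are recorded at all is open. Section V.10 has metal objects removed before the magnet and does not mention the sensor. If it comes off and is not replaced, the first wear also ends at week 0, and only the 11 drip hours remain. An analyst who knows which subjects were admitted would set those hours aside as inpatient infusion data. Doing so by ending the window at admission for everyone leaves about 6.4 days of the first wear (day -7 to 6 PM on day -1). Against 14 days, the standard error of a subject's mean rises by √(14/6.4) = 1.48 if days are independent (assumed).

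**Conclusion.** No change to the plan follows. The missing window is a gap that analysts fill sensibly with the pre-scan, pre-treatment days that every version of the schedule provides.

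On that choice the overlap with treatment contributes nothing. What could remain is 6.5% to 9.4% attenuation of the change in 7-day mean glucose for subjects clamped at both visits, and only if their infusion hours are kept. The one-visit cases, 13.7% smaller or 4.4% larger, rest on assumed means of 200 and 150 mg/dL. Apart from a subject clamped at week 12 only, the error runs toward understating improvement. A fall in glycemia large enough to matter for the study's aim would still be seen.

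The exposure is also narrow. CGM shares endpoint (a) with HbA1c, which does not depend on the sensor window. The stated aim is polyol pathway activity, measured by brain fructose and glutathione, and that is unaffected. Section V.12 already disclaims definitive testing.

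The 3 h and 4 h clamp durations in Section V.3 contradict each other and must be reconciled as a matter of conduct. Here they only move the 7-day share from 8.8% to 9.4%. The conclusion assumes that mean glucose is the metric and that intensification does not begin before week 0.
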